Non-Damaging Photothermal Therapy of Non-exudative Age
Related Macular Degeneration

Study Protocol and Statistical Analysis Plan
NCT02569892

August 15, 2018

Title:

Non-Damaging Photothermal Therapy of Non-exudative Age Related Macular Degeneration

Introduction

Age Related Macular Degeneration (AMD) is the leading cause of blindness and visual disability among patients exceeding 60 years of age in the western hemisphere. The clinical presentation of AMD ranges from soft drusen in patients with normal visual acuity to geographic atrophy or subfoveal choroidal neovascularization (CNVs), disciform scarring and eventually legal blindness.¹

Approximately 10 to 15% of patients with AMD develop severe visual loss due to geographic atrophy characterized by the atrophy of retinal pigment epithelium, choriocapillaris and outer retina or due to exudative AMD. Nonexudative AMD is responsible for about 25% of the severe visual loss and the remaining is caused by neovascular AMD². Fortunately, with the introduction of pharmacological anti-VEGF treatments to neovascular AMD, exudative AMD can be effectively treated, thereby maintaining good visual acuity for extended period of time. However, there is still no treatment for nonexudative AMD other than vitamin supplementation, and patients inevitably progress to advanced disease and associated visual loss.³

The cumulative incidence of new exudative or atrophic lesions in eyes initially free of advanced AMD has been estimated as 8.6% at one year, 16.4% at two years and 23.5% at three years.⁴ The five-year risk of CNV occurrence in the fellow eye of patients who have already experienced CNV in the first eye, varies from 7% to 87% depending on the coexistence of four main risk factors (presence of five or more drusen, focal hyperpigmentation, one or more large drusen and systemic hypertension).

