- **Safety Assessments.** Safety of the treatment will be assessed for ocular adverse event incidence (AEs) and serious AEs (SAEs), based on the reports of the patients and examination during or between visits until the month 24 of follow up. After 24 months, subjects will then be followed for an additional 3 years for observation
- **Serious adverse events (SAEs)** will be monitored continuously.

STUDY METHODS

Design:

- Prospective, Randomized Clinical Trial (RCT).
- 24 months with an additional 3 year observation follow up period. Subjects will be seen once a year and undergo non-invasive testing.
- Total patient recruitment 56 patients.
- Number of arms: 2 arms.
- Number of patients: 28 patients in each arm.

Patient Recruitment

1. Initial Assessment

The study will enroll 56 eyes in total. Patients will be initially assessed as part of their standard management and, if fulfilling all the inclusion criteria, will be referred to a Study Investigator.

At the initial assessment, the investigator will confirm that the patient has satisfied the eligibility criteria stated in the Study Protocol (SPR) and the study will be discussed in full with the study participant (SP). If interested in participating, the SP will be given a written informed consent to take home for further consideration. The patient will have a minimum of 24 hours to decide whether or not to take part in the study. All study procedures, will be explained to the SP by the investigator or staff member. The nature of the study will be also explained to the SP together with hazards of the study procedures, including any possible adverse events. The SP will be informed that he or she is free to terminate participation in the study for any reason.

Any patient unwilling to participate at this stage will be managed as part of the appropriate routine eye care pathway.

The study patient will undergo the Examination Procedures at the Baseline visit. The data from these tests will be used for study data analysis.

2. Examination Procedures at Baseline and Follow-up visits

- (1) ETDRS best corrected visual acuity.
- (2) Slit lamp biomicroscopy: dilated fundus examination with 78D Volk lens, intraocular pressure by Goldmann applanation tonometry.
- (3) Spectral domain OCT (Cirrus SD-OCT): Macular/macular cube/Volume scan & average central retina thickness and Drusen volume.
- (4) Fundus photography and autofluorescence.

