The treatment will be randomised at this stage, and the SP will be allocated to arm A (treat) or arm B (observe). The 56 eyes will be randomly allocated to each of the two study arms, 28 in each arm. The SP will be given a trial number, and the treatment record will be coded. **For patients where both eyes meet eligibility criteria both eyes will be enrolled with the Right Eye randomly assigned to active treatment arm or sham arm, with the Left Eye assigned to the opposite arm.**

3. Treatment Visit:

The SP will undergo treatment within 14 days after the examinations are performed.

Patient-eligibility

Inclusion criteria:

1. Older than 60 years of age.
2. Male or female patients with nonexudative AMD with a drusen volume of at least 0.03mm³ on OCT within the central 3mm circle centered on the fovea.
3. Adequate pupil dilatation and clear media to perform color, red-free imaging, fundus autofluorescence imaging, and OCT imaging.
4. Able to give an informed consent.

Exclusion criteria:

1. Presence of signs of advanced AMD, such as CNV, haemorrhages or macular atrophy based on OCT and FAF.
2. Previous macular laser treatment.
3. Any previous ocular condition that may be associated with a risk of developing macular oedema.
4. Vitreomacular traction determined clinically and /or by OCT, which in the opinion of the investigator contributes to the macular oedema (associated or causing a detachment of the fovea).
5. Presence of other macular disease such as epiretinal membrane, macular telangiectasia.
6. Ocular or periocular infections.
7. Planned intra-ocular surgery within one year.
8. Patient is unavailable for follow-up visits.

Study Examination Procedure

Baseline:

1. Full patient history including age, gender, ethnic group, diabetes history, medical history, medication history, ocular history, driving history, smoking status.

Baseline and Follow-up visits (see table):

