At the end of the 24 month period there will be an additional 3 year follow up. During the 3 year follow up, there would be no active component, the subjects will be seen once per year and undergo visual acuity testing and non-invasive retinal imaging to monitor for long term effects of treatment. This should not place a significant burden on the subjects since they are typically seen every 6 to 12 months for routine follow-up.

Best-corrected visual acuity (BCVA) using ETDRS charts at a distance of 4 meters, digital fundus photography, fundus autofluorescence, ocular coherence tomography (OCT), ocular coherence tomography angiography (OCTA when available on the site) will be carried out at baseline and at each follow-up visit.

TEST, treatment	Baseline	0	1 optional	3	6	12	18	24
Laser treatment		x			x	x	x	x
ETDRS visual acuity (BCVA)	x	x	x	x	x	x	x	x
Slitlamp	x	x	x	x	x	x	x	x
OCT	X	X	X	X	X	X	X	X
OCTA*	X	X	X	X	X	X	X	X
Digital Fundus Photography	X	X	X	X	X	X	X	X
Fundus autofluorescence	X	X	X	X	X	X	X	X

*OCTA will be done if available on site

STUDY RANDOMIZATION PROCEDURE

The subjects will be allocated to each arm of the study with simple randomization method using a computer-generated randomization list and sequentially numbered, sealed, opaque envelopes (SNSOE).

After a subject has signed informed consent, their name will be written on the selected envelope by the Clinical Trials Coordinator. The 56 eyes will

be randomly allocated to one of the two arms. The computer randomization will be done by the Clinical Trials Coordinator. The randomization table will be given to an independent person, who will sequentially label 56 envelopes, and enclose the written treatment type within the envelope. The study arm will be coded numerically for each subject.

METHOD OF STATISTICAL ANALYSIS

The data will be analysed using analysis of covariance, adjusting for baseline and disease severity. Results will be presented as differences between the treatment arms with their associated 95% confidence intervals, and non-significant effects interpreted in the context of these and the limited power of the study.

SAMPLE SIZE:

We estimated our sample size based on previous comparable publications that included approximately 50 eyes on average.¹¹⁻¹²

EFFICACY MEASURES:

Primary Outcome:

- Reduction in drusen volume in arm A compared to arm B.

Secondary Outcomes:

- Mean change in visual acuity (ETDRS letters)

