- Mean change in average central retinal thickness (ACRT) after 12, 18, 24 months of follow up.
- The proportion of patients with ACRT < 300 µm on Spectral domain OCT after 12, 18, 24 months of follow up
- Conversion into GA or CNV

SAFETY MEASURES:

- Monitoring of adverse events (AEs) and serious adverse effects (SAEs) (the incidence of ocular AEs and SAEs).
- Assessment of the retinal autofluorescence to identify any laser burn.
- Signs of any laser burn identified at RPE-photoreceptors layers on DRI-OCT.

ADVERSE EFFECTS:

- Any medical incidence in patients who received laser that could be associated with the treatment delivered in the research study.
- Any temporal or transitory adverse effect that has relationship to the study therapy.

REPORTING ADVERSE EVENTS (AE) AND SERIOUS ADVERSE EVENTS

- With any AE, we will treat the SP as appropriate to prevent further complications and to potentially resolve the event.
- SAEs and AE will be reported immediately (when the subject is in the office, if possible or within 24 hours of learning of the event) to the principal investigator, study coordinator and sponsor. The SP subject will be referred for further medical treatment if required.
- Follow-up reports on AEs should indicate whether the AE is presumed to be device-related, or a result of other factors, and should be recorded on the Adverse Events Report. The Adverse Events Report should be completed each time the subject is seen during the management of the incident and at resolution of the incident.
- All AEs occurring from the time of written informed consent throughout the course of the study (end of study is defined as the end of the scan acquisition) will be recorded at the study site.
- The AE should be made to describe it in terms of a diagnosis. If a clear diagnosis has been made, individual signs and symptoms will not be recorded unless they represent atypical or extreme manifestations of the diagnosis, in which case they should be reported as separate events. If a clear diagnosis cannot be established, each sign and symptom must be recorded individually.

All the adverse events shall be recorded in detail as specified below:

Name (Type)	The common name of the adverse event that appeared shall be written down.	
Date of onset	The first date that the physician in charge found the adverse event shall be written down.	

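### Fellow eyes of bilateral patients go to opposite arms, but the planned ANCOVA has no patient or pair term: its 95% intervals are too wide if pairs are enrolled and stay positively correlated

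*Combined protocol and SAP*

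**What the plan says.** Under Patient Recruitment, item 2, the randomisation paragraph fixes the size in eyes: "The 56 eyes will be randomly allocated to each of the two study arms, 28 in each arm". For a patient with two eligible eyes, it enrols both and has the "Right Eye randomly assigned to active treatment arm or sham arm, with the Left Eye assigned to the opposite arm". This is a rule, not an option.

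The section METHOD OF STATISTICAL ANALYSIS names a single model: "The data will be analysed using analysis of covariance, adjusting for baseline and disease severity". It continues: "Results will be presented as differences between the treatment arms with their associated 95% confidence intervals", with "non-significant effects interpreted in the context of these and the limited power of the study". No section mentions a patient effect, a paired analysis, a clustered variance or between-eye correlation.

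The Design list under STUDY METHODS counts patients instead: "Number of patients: 28 patients in each arm", 56 in all. The Initial Assessment paragraph that follows counts 56 eyes. Among the secondary outcomes, one is worded "The proportion of patients with ACRT" below 300 µm.

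**The concern.** Opposite-arm allocation makes each bilateral patient a matched pair. Two eyes of one person usually share something that baseline and severity do not explain. When they sit in opposite arms, the shared part cancels from the arm difference. An ANCOVA that treats the eyes as independent does not credit that cancellation and reports the standard error of an unpaired comparison.

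The plan relies on these intervals to read a non-significant result. If they are wider than the design warrants, a real effect can look inconclusive. Sample size was set by precedent, with no effect size, SD or power, so precision should not be given away. If the residual correlation were negative, the error would run the other way and the intervals would claim too much.

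**Working it through.** **Inputs from the documents.** 56 eyes, 28 per arm; fellow eyes in opposite arms; ANCOVA on baseline and disease severity; 95% intervals. The plan gives no figure to reproduce on this point.

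**Assumptions.** The number of pairs m (0 to 28) and the residual between-eye correlation rho (main range 0.2 to 0.7; also 0 and −0.2). Residual SD is set to 1.

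**Step 1: reported against true standard error.** Each arm mean has variance 1/28. The m pairs give the two means a covariance of m·rho/28². Hence

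Var(difference) = 2/28 − 2·m·rho/28² = (2/28)·(1 − rho·m/28).

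The independence model reports about 2/28, so

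reported SE / true SE = 1/√(1 − rho·m/28).

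Example: m = 14, rho = 0.5 gives 1/√(1 − 0.25) = 1/√0.75 = 1.155.

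Each cell shows this ratio, then the simulated coverage of the nominal 95% ANCOVA interval (4,000 runs per cell, two eye-level covariates with between-eye correlation 0.5, Monte Carlo error about 0.35 points):

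| Pairs | rho −0.2 | rho 0 | rho 0.2 | rho 0.5 | rho 0.7 |
|---|---|---|---|---|---|
| 7 | 0.976; 94.4% | 1; 95.3% | 1.026; 95.7% | 1.069; 96.4% | 1.101; 96.7% |
| 14 | 0.953; 93.8% | 1; 94.6% | 1.054; 96.1% | 1.155; 97.5% | 1.240; 98.4% |
| 28 | 0.913; 92.7% | 1; 95.2% | 1.118; 97.3% | 1.414; 99.0% | 1.826; 99.9% |

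With no pairs the ratio is 1 throughout. The formula ignores covariates and slightly overstates the effect: a separate simulation with covariates gave 1.135 for 14 pairs and 1.376 for 28 pairs at rho 0.5.

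**Step 2: is the estimate itself less efficient?** This is a separate question. With rho known, an estimate that uses the pairing has variance

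1 / [m/(2(1 − rho)) + (28 − m)/2].

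For m = 14, rho = 0.5 this is 1/(14 + 7) = 0.0476. The ANCOVA estimate has (2/28)·0.75 = 0.0536. The SE ratio is √(0.0536/0.0476) = 1.061. Over rho 0.2 to 0.7 the ratio is 1.005 to 1.143 with 7 pairs, 1.006 to 1.187 with 14, and exactly 1 with 28. When rho must be estimated, the simulated ratios are 0.98 to 1.09, 0.99 to 1.17 and 1.00 to 1.02. So with 7 pairs and rho up to 0.5 the estimate gains nothing. With all eyes paired, the ANCOVA estimate loses almost nothing (none without eye-level covariates, about 2 to 3% at rho 0.7 with them), and the main error is in the reported interval.

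**Step 3: what a corrected model returns.** A REML model with compound-symmetry residual covariance and Kenward-Roger correction covered 94.4 to 95.4% in all 15 cells. Without the small-sample correction, REML intervals covered only 90.7 to 94.3%. ANCOVA interval width divided by corrected width, for rho 0.2 to 0.7, was 1.00 to 1.16 with 7 pairs, 1.03 to 1.39 with 14 and 1.09 to 1.75 with 28. Power for an assumed 0.5 SD effect, ANCOVA against corrected model:

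| Pairs | rho 0.2 | rho 0.5 | rho 0.7 |
|---|---|---|---|
| 7 | 0.43 / 0.43 | 0.44 / 0.50 | 0.43 / 0.55 |
| 14 | 0.44 / 0.46 | 0.44 / 0.57 | 0.43 / 0.72 |
| 28 | 0.43 / 0.51 | 0.43 / 0.70 | 0.42 / 0.89 |

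**The case against.** *There may be no pairs.* With m pairs, 56 eyes come from 56 − m patients, so the Design list's 56 patients, read literally, leaves m = 0 and no effect. This does not dispose of the point, because the randomisation paragraph requires bilateral enrolment. It does show that the two counts conflict and that the size of the effect cannot be fixed from the documents.

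*The plan is brief rather than wrong.* An ANCOVA can carry a patient factor, and the text does not rule one out. But it names its adjustments, and patient is not among them. An analyst who follows it will treat fellow eyes as unrelated.

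*The error is cautious.* This stands for positive rho: type I error is not inflated. It does not hold for negative rho.

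*The remedy was checked only under favourable conditions.* This stands. The simulations assume equal residual variance in both arms and compound symmetry. Unequal variances and skew were not examined, so the Kenward-Roger model is an example of a suitable method, not the only one.

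*Stronger readings that the documents do not support.* A reader might infer that the missing term explains the study's low power. It does not: 56 unrelated eyes have power of only 0.451 for an assumed 0.5 SD effect, which follows from the size of the study. A reader might also carry the argument over to the yes/no outcomes and recommend a patient-clustered interval for the risk difference. The Introduction's own rates ("estimated as 8.6% at one year, 16.4% at two years and 23.5% at three years") argue against that as a general rule. With the two-year 16.4% as control rate, and 16.4% or an assumed 8.2% treated, such an interval covers 94.1 to 96.1%. At the one-year 8.6%, against an assumed 4.3% treated, it covers only about 80 to 91%. With 28 pairs and latent correlation 0.8, it covers about 80%, against about 92% for the unclustered interval.

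**Conclusion.** The concern holds conditionally. The design creates matched pairs, and the stated model ignores them. If pairs are enrolled, its 95% intervals are too wide for rho > 0 and too narrow for rho < 0. With no pairs or rho = 0 they are unaffected. The treatment estimate is unbiased in every case.

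The direction follows from the allocation rule and is firm. The size is not: the pair count and rho are both assumed. With 7 pairs and rho 0.2 the reported SE is under 3% too large and correcting it gains nothing. The largest figure, 1.83, needs all 28 pairs and rho 0.7. The point should be fixed because the remedy is cheap and the plan reads null results from these intervals. It does not invalidate the trial.

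**What to change.** In METHOD OF STATISTICAL ANALYSIS, replace the ANCOVA sentence with text to this effect: at each time point the eye is the unit of analysis; a linear model includes arm, the eye-level baseline value and disease severity, and allows within-patient correlation between fellow eyes, with a small-sample correction (for example REML with compound-symmetry residual covariance, which permits negative correlation, and Kenward-Roger degrees of freedom). Paired and single eyes are all included. Results are arm differences with 95% intervals, reported with the number of bilateral patients and the estimated between-eye correlation. Disease severity, which the documents do not define, should be defined in the same place.

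Two related edits: reconcile the 56 patients in the Design list with the 56 eyes given elsewhere, and state the yes/no outcomes per eye, since a bilateral patient belongs to both arms. Do not adopt the patient-clustered risk-difference interval as a general method for those outcomes.

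Cost: one paragraph and slightly more analysis work, with no added patients, visits or data. If rho is zero, intervals are 1.7 to 1.9% wider than the ANCOVA's and power for 0.5 SD is 0.7 to 1.6 points lower.

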Micropulse laser photocoagulation avoids the excessive heating which causes visible burns, tissue necrosis, and related collateral effects¹³, while providing similar clinical benefits as conventional laser coagulation.¹⁴⁻¹⁹ However, the lack of a reliable titration for every patient and absence of visible endpoint makes it difficult for the physician to (a) know which retinal areas have been treated and (b) to ensure the adequate amount of laser energy in the treatment. In addition, the dense coverage of the retina with the sub-visible laser exposures typically requires more than 500 spots in the macula, which is difficult to accomplish without pattern scanning laser. These issues prevented acceptance of this technology in clinical practice.

We have developed the titration protocol for PASCAL laser, which ensures that pulse energy is within the range of clinical efficacy, but does not exceed the tissue damage threshold²¹ in every patient. This protocol, called EndPoint Management, has been recently tested in a clinical trial, which demonstrated its safety and efficacy in treatment of Central Serous Retinopathy²² using 30% energy settings. The trial demonstrated lack of tissue damage and excellent tissue response to the treatment, even after multiple retreatments. The average retreatment period in this trial was found to be 6 months.

We propose to use the same laser parameters for treatment of the macula in patients with early AMD to prevent drusen growth and advancement of the disease into geographic atrophy or neovascularization.

AIMS OF THE STUDY

1. To determine whether photothermal therapy (PTT) of the macula with EpM® reduces the volume of drusen in the macula.
2. To determine whether PTT decreases the incidence of advanced AMD (neovascular AMD or geographic atrophy).

The primary efficacy outcome measure will be the reduction in drusen volume in the central 3mm circle over 12, 18, 24 months in subjects treated with PTT, compared to observation alone.

The secondary efficacy outcomes after the month 12, 18, 24 of follow up will be:

- **Functional outcome:**
 - Mean change in visual acuity in both groups.
- **Anatomical outcome:**
 - Reduction of drusen growth;
 - Prevention of neovascular AMD;
 - Prevention of geographic atrophy based on OCT and FAF.

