Causal relation	Write down probable causes, and classify the causal relation with the test device depending on the presence or absence of the causal relationship as defined below. The adverse events that are judged to have no relation with the test devices are classified as complications; all the others are classified as adverse device effects.	
	Probably not related	The adverse event is definitely related to other than the test device. (Complication)
	Possibly related	The adverse event is possibly related to the test device; the causal relationship with the test devices is fully undeniable. (Adverse device effect)
	Probably related	The cause of the adverse event cannot be located. However, the adverse event is probably related to the test device. (Adverse device effect)
	Definitely related	The adverse event is definitely related to the test device. (Adverse device effect).
Severity	The severity shall be classified into mild, moderate and severe based on the criteria:	
	Mild	The symptom is mild and expected to heal soon.

	Moderate	The symptom is described as neither mild nor severe.
	Severe	The finding is serious and expected to interfere with the subject's daily life depending on the subject's physical predisposition or the circumstances under which the adverse event appeared.
Symptom, progress and treatment	Necessity for treatment and progress from the detection of the adverse event and the determination of outcome shall be written down.	
Outcome	The classification into "healed", "unchanged", "aggravated", or "death" and the outcome date shall be written down. If the subject died, statement of death shall be made.	
Views on the adverse event	Views on the adverse event by the physician in charge shall be written down. Omission is allowed if there are no special comments.	

POTENTIAL RISKS:

- Complications of conventional laser therapy including marked vision loss, paracentral scotomas or accidental application of laser in the fovea. There is limited data regarding potential risks of photothermal therapy, however, due to its non-damaging nature, it is expected to be safer than conventional photocoagulation.

STUDY PATIENT DISPOSITION

Completed SP: A completed SP is one who has not been discontinued from the study and has completed all study related procedures.

Discontinued SP: SP may be discontinued prior to their completion of the study due to:

- subject request
- adverse events
- protocol violations

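### No safety measure or adverse-event threshold uses BCVA, and its only stated analysis is a mean change, so a few eyes with severe vision loss would show only if recorded as adverse events or as GA/CNV conversion

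*Combined protocol and SAP*

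**What the plan says.** Under AIMS OF THE STUDY, the functional secondary efficacy outcome at months 12, 18 and 24 is "Mean change in visual acuity in both groups". EFFICACY MEASURES repeats it as "Mean change in visual acuity (ETDRS letters". PATIENT FOLLOW-UP and its visit table schedule BCVA at baseline and at all later visits, months 3 and 6 included. Yearly acuity tests follow in the three-year extension, to watch for late effects, with no analysis attached.

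SAFETY MEASURES has three items: monitoring of adverse events ("the incidence of ocular AEs and SAEs"), "Assessment of the retinal autofluorescence to identify any laser burn", and "Signs of any laser burn identified at RPE-photoreceptors layers on DRI-OCT". None refers to BCVA.

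AIMS OF THE STUDY says that ocular adverse events are assessed "based on the reports of the patients and examination during or between visits until the month 24 of follow up". Under REPORTING ADVERSE EVENTS, once there is a clear diagnosis, "individual signs and symptoms will not be recorded unless they represent atypical or extreme manifestations of the diagnosis". Such manifestations are reported as separate events. Where no clear diagnosis can be made, every sign and symptom is recorded.

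POTENTIAL RISKS lists "Complications of conventional laser therapy including marked vision loss, paracentral scotomas or accidental application of laser in the fovea". It adds that data on the risks of photothermal therapy are limited and that the treatment is expected to be safer than conventional photocoagulation.

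**The concern.** If the laser harms vision, the likely pattern is a large loss in a few eyes, not a small shift in the whole arm. A mean over 28 eyes is a poor summary of that pattern. BCVA at months 3 and 6 is collected, but no analysis is tied to those visits.

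That leaves adverse-event reporting and the conversion outcome to carry individual losses. The adverse-event route depends on judgement. No letter loss triggers a report, the grade for a severe event rests on interference with daily life, and a vision loss can be absorbed into a diagnosis. Fellow eyes of one patient may also be in opposite arms, yet the listed adverse-event fields include neither the eye nor a BCVA value.

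At stake is whether the report can say how many eyes in each arm lost substantial vision. Without a count, a small mean difference may be all that the reader sees of visual safety.

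**Working it through.** **Inputs from the document.** 28 eyes per arm, 2 × 28 = 56 in total, which agrees with the stated total. SAMPLE SIZE rests on earlier studies of about 50 eyes and gives no power, effect size or SD, so there is no calculation to reproduce. The planned 95% intervals are read as two-sided.

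**Assumptions.** The SD of BCVA change is 6 to 10 letters (not in the document). Eyes are independent, there is no dropout, and the affected laser eyes each lose an extra 15 or 30 letters.

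**Precision of the mean difference.** Half-width = t(0.975, 54) × SD × √(2/28), with t = 2.005.
- SD 6: SE 1.60, half-width 3.2 letters
- SD 8: SE 2.14, half-width 4.3 letters
- SD 10: SE 2.67, half-width 5.4 letters

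**Shift of the mean.** If k of 28 laser eyes each lose L letters, the arm mean moves by k × L / 28. For example, 2 × 15 / 28 = 1.1 and 3 × 15 / 28 = 1.6. The chance that a two-sided 5% t-test flags the difference was simulated with 20,000 runs per row and SD:

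| Eyes × letters lost | Mean shift | SD 6 | SD 8 | SD 10 |
|---|---|---|---|---|
| 2 × 15 | 1.1 | 7.0% | 6.1% | 5.7% |
| 3 × 15 | 1.6 | 10.4% | 8.5% | 7.4% |
| 2 × 30 | 2.1 | 8.7% | 8.0% | 7.6% |
| 3 × 30 | 3.2 | 16.8% | 13.9% | 12.1% |
| 4 × 30 | 4.3 | 30.3% | 23.5% | 19.2% |

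The chances stay low partly because the large losses also inflate the variance. A normal approximation that ignores this gives higher values (3 × 30 at SD 6: 52%), but stays below 80% in every case tried.

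**Is a few eyes a plausible number?** The Introduction cites CNV in 6 of 63 eyes with visible burns within 3 months: 6/63 = 9.5%, and 9.5% of 28 is about 2.7 eyes. This only illustrates scale. The same text reports no such CNV with subthreshold treatment, and CNV would here be counted as conversion.

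**What a count would give.**
- 2/28 is 7.1%, exact 95% interval 0.9% to 23.5%.
- 3/28 is 10.7%, interval 2.3% to 28.2%.
- 0/28 has a two-sided 95% upper limit of 1 − 0.025^(1/28) = 12.3%.
- As a test, Fisher's two-sided p against 0/28 is 0.49, 0.24, 0.11, 0.051 and 0.023 for 2 to 6 eyes. Six against none is needed for p < 0.05.

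**Chance crossings of a cut-off.** With normal change, mean 0 and SD 8:
- A loss of at least 10 letters has probability P(Z ≤ −1.25) = 10.6%, or about 3 of 28 eyes per arm at each visit (1.3 at SD 6, 4.4 at SD 10).
- A loss of at least 15 letters is expected in about 0.9 of 28 eyes.

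**The case against.** The strongest reply is that the plan has other routes to an individual loss.

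- Ocular adverse events are sought by patient report and examination, and BCVA heads the list of examination procedures.
- The diagnosis rule merges a symptom into its diagnosis, but the diagnosis is still an event. Extreme manifestations are separate events, and severe vision loss is a natural candidate.
- Loss through GA or CNV is counted as conversion.
- Autofluorescence and OCT look for burns, including an accidental foveal one.
- METHOD OF STATISTICAL ANALYSIS already says that non-significant results will be read with their intervals and the study's limited power.
- The SD is assumed. Baseline adjustment and paired fellow eyes would change the SE.

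Most of this stands, and it rules out three stronger readings that a reader might infer. The first is that severe losses would not show at all, or would vanish as events. The routes above contradict that. The second is that mean change is the only use of BCVA. It is the only stated statistical analysis, but the extension's acuity tests serve monitoring. The third is that marked vision loss is a stated risk of the study laser. POTENTIAL RISKS attaches it to conventional laser.

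The reply does not remove the gap. No route rests on the measured letters, and a careful reading of an interval for a mean does not show which eyes lost vision. Pairing or baseline adjustment changes the SE, but not the dilution k × L / 28 in the unadjusted mean.

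**Conclusion.** The point holds in a limited form. No safety measure or adverse-event threshold uses BCVA, and mean change is its only stated statistical analysis. A few eyes with severe loss would show only if recorded as adverse events or as conversion. The gap is a large loss that reaches neither route.

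The mean would very probably miss such eyes. Two or three losing 15 letters shift it by 1.1 or 1.6 letters, against a half-width of 3.2 to 5.4. Even three eyes losing 30 letters are flagged in only 12% to 17% of simulated trials. These figures rest on the assumed SD of 6 to 10 letters, independent eyes and no dropout. The absence of BCVA from the safety measures rests on the text alone.

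The remedy is worth making because it is a better summary of harm at almost no cost. It does not make the trial able to test for a difference in severe vision loss.

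**What to change.** Add one item to SAFETY MEASURES: the number and percentage of eyes in each arm with a BCVA loss of at least 15 letters from baseline, at every scheduled visit including months 3 and 6. Give exact 95% intervals and use the eyes measured at that visit as the denominator. Add a listing of each such eye with its arm, cause and time since the last session. Month 9 is in the PATIENT FOLLOW-UP text but not in the visit table, so settle the list of visits first.

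Say that 15 letters is a conventional cut-off, since the document sets none. Label the table descriptive, because 28 eyes per arm give little formal power. A 10-letter count is optional and should carry a note that at SD 8 about 3 of 28 eyes per arm would cross it by chance. Keep mean change as the efficacy outcome.

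The cost is wording in the protocol and SAP, plus one table and one listing. BCVA is already collected, so no new visit, test or staff is needed, and treatment is unchanged.
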